7.3 Withdrawal Visit

If a subject terminates the study early for one of the reasons listed in Section 5.5 or 5.6, and is willing to return to the site for a final study visit, the following will be completed:

- Record adverse events as reported by subject or observed by investigator
- Provide final instructions to subject (e.g., follow-up of ongoing adverse events)

If the subject cannot be reached or is not willing to return to the study site for a final study visit, the subject will be considered lost to follow up.

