5.5 Subject Withdrawal

5.5.1 *Reasons for Withdrawal*

Subjects are free to withdraw from participation in the study at any time upon request. An investigator may terminate a study subject's participation in the study if:

- Any clinical adverse event (AE), laboratory abnormality, or other medical condition or situation occurs such that continued participation in the study would not be in the best interest of the subject.
- The subject meets an exclusion criterion (either newly developed or not previously recognized) that precludes further study participation.

5.5.2 *Handling of Subject Withdrawals or Subject Discontinuation of Study Intervention*

Subjects wishing to withdraw from the study at any time may do so and should notify the study team. For payment to these subjects, see Section 5.3.

Withdrawals need not be replaced, but may be on a case-by-case basis, at the PI's discretion. The power calculations allow for a 20% dropout rate.

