9.2 Time Period and Frequency for Event Assessment and Follow-Up

Unanticipated problems will be recorded in the data collection system throughout the study.

The PI will record all reportable events with start dates occurring any time after informed consent is obtained until 7 (for non-serious AEs) or 30 days (for SAEs) after the last day of study participation. At each study visit, the investigator will inquire about the occurrence of AE/SAEs since the last visit.

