Any AE meeting the specified Serious Adverse Event criteria will be submitted on an SAE form to NIDCR's centralized safety system via Rho Product Safety. This report may be sent by fax or email. Once submitted, Rho Product Safety will send a confirmation email to the investigator within 1 business day. The investigator should contact Rho Product Safety if this confirmation is not received. This process applies to both initial and follow-up SAE reports.

SAE Reporting Contact Information:

- Product Safety Fax Line (US): [name]
- Product Safety Fax Line (International): [contact]
- Product Safety Email: [contact]

General questions about SAE reporting can be directed to the Rho Product Safety Help Line (available 8:00AM – 5:00PM Eastern Time):

- US: [name]
- International: [contact]

The study clinician will complete a Serious Adverse Event Form and submit via fax or email to NIDCR via Rho Product Safety within the following timelines:

- All deaths and immediately life-threatening events, whether related or unrelated, will be recorded on the Serious Adverse Event Form and submitted to Product Safety within 24 hours of site awareness.
- Serious adverse events other than death and immediately life-threatening events, regardless of relationship, will be reported by fax within 72 hours of site awareness.

All SAEs will be followed until resolution or stabilization.

The study clinician will report SAEs to the IRB in the Adverse Event form via eResearch system within the following timelines:

- All deaths and life-threatening outcomes that are related and unexpected should be submitted as soon as possible, but within 7 calendar days of site awareness.
- Serious adverse events other than death and life-threatening outcomes that are related and unexpected should be submitted within 14 calendar days of site awareness.
- Serious adverse events that are unrelated and expected should be submitted within 14 calendar days of site awareness.
- All other unrelated and unexpected events should be submitted in aggregate form in conjunction with completion of the scheduled continuing review.

9.4.3 *Reporting of UaPs and SAEs to NIDCR*

A copy of all SAE reports will be provided in a timely fashion to NIDCR/Rho Inc (see Section 9.4.2 for details).

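### Section 7.3 labels a reachable subject who declines the final visit 'lost to follow up', so a known withdrawal reason can be misclassified, and Sections 7 and 7.3 do not fit the adverse-event recording period in Section 9.2

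*Combined protocol and SAP*

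**What the plan says.** Section 7.3 sets its scope as "If a subject terminates the study early for one of the reasons listed in Section 5.5 or 5.6". For those who come back, it lists two tasks: recording adverse events and giving final instructions, with follow-up of ongoing events as the example. It then deals with those who do not come back, joining subjects who cannot be reached to subjects who decline: "not willing to return to the study site for a final study visit, the subject will be considered lost to follow up".

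The Section 5.5.1 reasons that feed this rule include an investigator's decision: "Any clinical adverse event (AE), laboratory abnormality, or other medical condition or situation occurs such that continued participation" is not in the subject's interest. Section 5.5.2 expects subjects who leave by choice to be in contact: "Subjects wishing to withdraw from the study at any time may do so and should notify the study team".

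Three other places govern adverse events around withdrawal:

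- Section 7 runs recording from consent until the subject leaves the study. It adds that events patients volunteer afterwards, if potentially linked to the procedures, will be documented.
- Section 9.2 records reportable events with start dates "until 7 (for non-serious AEs) or 30 days (for SAEs) after the last day of study participation".
- Section 9.4.2 states: "All SAEs will be followed until resolution or stabilization". It makes no exception for subjects who have withdrawn.

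In Table 2 the Early Termination column carries adverse events and no questionnaires. Its footnote limits it to subjects who complete an in-person visit.

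**The concern.** Lost to follow-up normally means that contact has failed and that neither the outcome nor the reason for leaving can be established. Section 7.3 gives the same label to someone the team can still telephone and whose reason it may already hold. If the label becomes the disposition category, a subject withdrawn for an adverse event who will not travel is filed with the unreachable. Discontinuation by reason and arm is a basic description of tolerability in a two-arm sham-controlled trial, and it is hard to rebuild once the reason has been replaced by a neutral code.

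The second matter is practical. The early-termination tasks sit inside a visit that this subject does not attend, and the plan describes no other contact. Staff working from Sections 7 and 7.3 would have no stated way to obtain the information that Section 9.2 asks for after participation ends.

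**Working it through.** **The one relevant figure.** Section 12.2 plans 24 evaluable subjects per group and a 20% drop-out rate. 24 / (1 − 0.20) = 30 per group, which reproduces the plan's number. Over both groups the allowance is 60 × 0.20 = 12 subjects. It covers all causes, so relabelling a withdrawal leaves it unchanged. Within it, anywhere from 0 to 12 subjects could be reachable people who decline the visit. The documents give no split by reason, so the range cannot be narrowed.

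**Who receives the label.** The rule turns on one 'or': "If the subject cannot be reached or is not willing to return to the study site for a final study visit, the subject will be" classed as lost. Taking the possible cases in turn:

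| Subject who stops early | Reason for stopping | Status under 7.3 |
|---|---|---|
| Attends the final visit | Can be known | Not labelled lost |
| Reachable, declines the visit, investigator ended participation for an adverse event | Known | Lost to follow up |
| Reachable, declines the visit, withdrew by notifying the team | Known if given; Section 5.5.1 does not require one | Lost to follow up |
| Cannot be reached | May be unknown | Lost to follow up |

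The second row is misclassified by the wording of the rule, and the third is whenever a reason was given. Only the fourth fits the label.

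**Adverse-event text side by side.**

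| Section | When or how events are captured | Reaches a subject who declines the visit? |
|---|---|---|
| 7 | Until the subject leaves the study; later only if volunteered and potentially procedure-related | Not actively |
| 7.3 and Table 2 footnote | At an in-person final visit | No |
| 9.2 | Start dates up to 7 days (non-serious) or 30 days (serious) after last participation; inquiry is described at study visits | Required, but no contact route given |
| 9.4.2 | Serious events followed to an end point | Required, but no contact route given |

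Sections 7 and 9.2 give different end dates for recording, and Section 7.3 offers no means of meeting the later one. For serious events the duty itself is clear. For non-serious events still ongoing at withdrawal, the follow-up instruction appears only as a task of the visit the subject has declined.

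**The case against.** The strongest reply is that 7.3 attaches a follow-up label and nowhere says that it overwrites the reason for withdrawal. The text contains no disposition table and no reason-coding rule. Section 12.4 defers the final analysis to the SAP, and Section 18 lists the SAP, case report forms, Manual of Procedures and DSMB charter as separate documents. A form not shown may already capture the reason. This stands: the supportable statement is that reasons can be misclassified, and a reader who infers that withdrawals will be miscounted goes further than the documents.

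A reader might also infer that safety follow-up stops once the label is applied. For serious events Section 9.4.2 contradicts this, and Section 9.2 keeps recording open for 7 or 30 days. A label and a continuing duty can coexist. What remains is the unmatched end date in Section 7 and the missing contact route.

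A third tempting inference is that the DSMB or the analysis of missing data would be misled. Section 3.2.3 solicits adverse events at every visit. Section 12 reports safety for all who had at least one session, and Section 12.3.1 summarizes events by treatment group, whatever the withdrawal label. VAS and GeoPain are taken before and after the stimulation sessions, so pain that worsens during treatment is recorded anyway. The efficacy model in Section 12.3.2.1 does not use withdrawal reason, and no missing-data analysis is described.

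Finally, worsening pain is not a named reason in Section 5.5.1; it would enter as an adverse event or as the subject's own request. Section 15.3 lets subjects withdraw consent at any time, so any remedy must respect a refusal of further contact.

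**Conclusion.** The point holds in a limited form. Section 7.3 states a rule that puts reachable subjects, some with a known reason, in the same category as the unreachable. Sections 7 and 7.3 do not fit the recording period in Section 9.2. The effect is on the disposition record and on the route for collecting late adverse-event information. No planned efficacy estimate and no sample-size figure changes.

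Its size is not known. The all-cause allowance of 12 of 60 caps the number affected only if dropout stays within plan, and it says nothing about the split by reason or arm. The conclusion assumes that the label would serve as the disposition category. If a form already keeps the reason alongside it, the first part is a matter of wording and the second is unaffected. This is a cheap improvement of minor severity.

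**What to change.** 1. In Section 7.3, reserve lost to follow-up for subjects who cannot be reached after documented attempts.
2. For all other early terminations, keep the recorded withdrawal reason as the disposition category whether or not the final visit takes place, and report discontinuation by reason and arm.
3. For a reachable subject who declines to travel and has not refused further contact, obtain the adverse-event information required by Sections 9.2 and 9.4.2 by telephone. A call before the 30-day period closes would not cover all of it.
4. Reconcile Sections 7, 7.3, 9.2 and 9.4.2 on when adverse-event recording ends and how it is done after withdrawal.

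The cost is a few sentences, a disposition code if the forms lack one, and one telephone call per affected subject. Any further contact about an unresolved serious event is already required by Section 9.4.2.

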7.4 Repeated Screening Visit

If a subject completes a Screening Visit (ie, signs informed consent), but does not complete a Randomization Visit (first session of HD-tDCS Week 1) within 3 weeks, the subject may continue participation by repeating a limited to full Screening visit.

Informed consent must be re-obtained if there have been changes to the informed consent document since the version that was originally signed. These changes might include:

- New “reasonably foreseeable” risks or side effects judged to be “definitely related” to the research.
- Changes are made to the protocol such as additional tests or research procedures that may affect subjects’ willingness to participate, rights, welfare, or safety.
- New information included that may affect subjects’ willingness to participate.
- A change in principal investigator and contact information.

The remaining Screening evaluations and questionnaires to be repeated are to be determined based on clinical relevance by the PI.

7.5 Unscheduled Visit

If a subject returns to the study site on a date that is significantly outside a visit window, the following assessments will be completed:

- Record adverse events as reported by subject or observed by investigator

8 STUDY PROCEDURES /EVALUATIONS

8.1 Study Procedures/Evaluations

8.1.1 *Quantitative Sensory Test (QST)*

For both TMD subjects and healthy volunteers, QST will be performed in four areas: right and left superficial masseter muscle, and dorsum of the hands.

Thermal stimulation: We will use a standard clinical evaluation program devised by MEDOC (Israel) on a thermal stimulation device of their design. The program is comprised of a series of hot and cold stimuli that are delivered from a baseline temperature of 32°C bilaterally. Subjects will control the heating/cooling unit with a computer mouse and they will be instructed to tap the mouse button at the first perception of pain. Each stimulus (hot and cold) will be delivered three times in each location, and the MEDOC program records the average temperature.

Algometry: We will use an algometer (Somedic, Sweden) to define pressure pain threshold and tolerance in the four regions bilaterally, and in a randomized fashion. Each area will be evaluated three times, and the ultimate pressure pain threshold and tolerance levels will be the average of the three measurements recorded. For the evaluation of motor function, we will perform the exam according to the DC/TMD guidelines and forms (e.g., range of motion).

8.1.2 *Sustained Masseteric Pain Model for TMD Research – Positron Emission Tomography and Hypertonic Saline Challenge*

Positron emission tomography (PET) scans with [¹¹C]carfentanil and infusion of hypertonic saline during the scan will be conducted twice during the study for each TMD subject and only once for each healthy volunteer.

PET scans will be used for the clinical trial with TMD patients to analyze potential changes in the brain occurring as a result of treatment with HD-tDCS, particularly potential changes in the thalamic μ OR availability in the brains of TMD patients during masseteric pain. In addition, we will investigate whether chronic TMD is associated with μ OR BP_{ND} changes as compared to healthy subjects during baseline PET (#1) session at rest, and during experimental sustained masseteric pain stress challenge.

A hypertonic saline challenge will be used to test the capacity of an individual to mobilize neurotransmitters involved in the response to pain. It is hypothesized that this response may be altered using HD-tDCS treatment in TMD patients. Hypertonic saline (5%; less than 5 mL over 20 minutes) will be infused into the masseter muscle by a computer-controlled closed loop system and a syringe pump⁴² during the PET scan, causing persistent pain that fluctuates in nature. The intensity of the pain will be controlled by the individual's experience such that individuals with chronic TMD pain will

experience the same subjective pain intensity as those without TMD. The system is calibrated to induce an average target VAS intensity of 40 units (0= no pain at all, 100= most pain imaginable) over 20 min (**Figure 7**).

Figure 7. Diagram of System to Induce and Maintain Pain Intensity. Block diagram to induce and maintain pain intensity between preset VAS scores by infusion of 5% hypertonic saline into the masseter during the PET session. The main feature of the adaptive control delivery system is a proportional-integrative-derivative (PID) controller. It corrects the difference between actual and estimated pain intensities. The adaptive element includes strategies to bring pain intensity back in case the preset bounds are exceeded and recalculates any previously established PID parameters.

Pain invariably disappears well within 5-10 min of infusion completion. The total volume of 5% hypertonic saline required to maintain the target pain intensity is also an objective measure of "sustained" pain sensitivity.

A 90min PET session of [¹¹C]carfentanil⁴³ will be performed, where 45min of baseline will be followed by a 45min challenge period, in which controlled moderate masseteric pain **will be induced for only 20 min**.

PET Protocol	Early Phase [¹¹ C]Carfentanil 5-40min	Late Phase [¹¹ C]Carfentanil 45-90min
TMD Active Group	Baseline	Masseteric Pain 20min
TMD Sham Group	Baseline	Masseteric Pain 20min
Healthy Control Group	Baseline	Masseteric Pain 20min

PET scans will be acquired with a Siemens HR+ scanner in 3-D mode (reconstructed FWHM resolution ~5.5mm in-plane/5.0mm axially) with septa retracted and scatter correction. Subjects will be positioned in the PET scanner gantry and two intravenous (antecubital) lines placed.

[¹¹C]carfentanil (CFN), a selective and specific μ -opioid receptor radioligand, is synthesized at high specific activity (> 2000 Ci/mmol) by the reaction of ¹¹C-methyl triflate with desmethyl carfentanil as previously described. 15 \pm 1 mCi are administered to each subject with a maximum mass injection of 0.03 μ g/kg to ensure that the compound is administered in true tracer quantities, eliminating significant receptor occupancy. The percent occupancy of μ -opioid receptors at peak regional carfentanil concentrations has been calculated at 0.2%-0.6% by utilizing the average mass of carfentanil administered and the known concentration of μ -opioid receptors in the postmortem human brain. Fifty percent of the [¹¹C]CFN dose will be administered as a bolus, and the remainder will be administered as a continuous infusion by using a computer-controlled automated pump to achieve steady-states between (non-)specific binding areas (5-7min post-tracer administration with Logan plots, and full equilibrium conditions and Logan plots at 40min post-tracer administration) for baseline (resting-state) and 20min of **masseteric pain challenge** for μ -opioid system activation analysis. Twenty-eight frames will be acquired over 90min.

Subsequently, dynamic image data for each of the receptor scans are transformed on a voxel-by-voxel basis into three sets of parametric maps, which are co-registered to each other. These are (1) a tracer transport measure (K_1 ratio, proportional to cerebral blood flow; tracer transport = blood flow \times tracer extraction) and receptor-related measures (non-displaceable binding potential, BP_{ND}), encompassing data from (2) 10-40 min (baselines) and (3) 45-90 post tracer administration (pain or saline control). These parametric images are calculated using a modified Logan graphical analysis (Logan et al., 1996) with the occipital cortex (a region devoid of μ -opioid receptors) as the reference region. The Logan plot becomes linear well within 10 minutes after the start of radiotracer administrations with a slope proportional to the $B_{max}/K_d + 1$ for this receptor site. B_{max}/K_d is the “receptor related” measure BP_{ND} . If noise-related underestimations in BP_{ND} measures are observed, these can be further corrected utilizing published methods⁴⁴. In addition, late scan periods will be assessed using ratios of specific to non-specific binding at full equilibrium [(specific –nonspecific)/nonspecific] to ensure that biases are not introduced by the use of Logan plots⁴⁵.

8.1.3 ***MRI Acquisition***

Magnetic resonance imaging (MRI), without contrast, will be conducted twice during the study on each TMD subject and only once on each healthy volunteer. MRI scans are acquired on a 3 T scanner (General Electric, Milwaukee, WI). These images provide anatomical information for structure identification and will be utilized for the anatomical standardization to the ICBM/MNI atlas coordinate system. This will establish the linear and non-linear warping transformation matrices to be applied to the co-registered receptor binding maps. The acquisition sequence is axial T1 FAST SPGR MR (TE = 3.4, TR = 10.5, TI = 200, flip angle 25 deg, FOV 24cm, 1.5mm thick slices, NEX = 1), acquisition matrix 256x256, 60 slices. T1-weighted MR and PET images of each subject are then co-registered to each other using a mutual information algorithm⁴⁶. For this purpose, K_1 ratio images are first aligned to the MR, and the transformation matrix

applied to the co-registered BP_{ND} scans of the same image set. The MR scans are then anatomically standardized to ICBM brain atlas stereotactic coordinates by non-linear warping, and the resulting transformation matrix applied to both K₁ ratio and BP_{ND} image sets^{47, 48, 49, 50}. As an alternative approach for Aim3, ¹H-MRS spectra will be collected from the ACC (3x2x3cm) based on our prior work showing Glx alterations in this region following tDCS therapy. Single-voxel point resolved spectroscopy (PRESS)(TR/TE=2000/35ms) will be performed using 'VAPOR' water suppression with 32 averages to measure Glx and NAA levels. A MEGAPRESS experiment, which edits out the overlapping creatine peak at 3.0ppm will measure GABA levels⁵¹. The MEGA-PRESS experiment will use: TE=68ms (TE₁=15ms/TE₂=53ms); TR=1.8s; 256 transients of 2k datapoints; spectral width=2kHz; frequency selective editing pulses (14ms) applied at 1.9ppm (ON) and 7.46ppm (OFF).

8.1.4 *Questionnaires*

To assess the primary effectiveness endpoint, clinical pain intensity at rest will be measured using the VAS at study visits shown in Table 2, Schedule of Events – II. Questionnaires. Other questionnaires listed in Table 2 will be used to address the secondary objectives of the study.

8.2 *Laboratory Procedures/Evaluations*

8.2.1 *Clinical Laboratory Evaluations*

Pregnancy and urine drug screen testing will be performed by dipstick analysis to assess eligibility criteria prior to PET scans #1 and #2.

8.2.2 *Blood Samples for Study-Specific Analyses*

If the subject consents to participate in this part of the study, serial blood samples that do not exceed a total of 45 mL (3 Tbsp) will be collected during each PET scan for analysis of inflammatory biomarkers. This blood will be collected from a separate intravenous line placed into the vein of the arm that is opposite the arm used for the tracer injection. Approximately 6 mL (0.4 Tbsp) of blood will be drawn during each PET scan at time 0, 20, 45, 65 and 80 for analysis of biomarkers. See details in MOP Section 6.6.3. The blood samples will be frozen for future testing to look at biological substances in the blood and potential hereditary traits associated with migraine.

One additional, individual collection for genetic analysis will be performed for future studies. The blood for genetic analysis will be collected prior to tracer administration and will not exceed 25 mL (2.4 Tbsp) per scan.

The total blood volume collected per scan will not exceed 70 mL per subject.

Details can be found in the Manual of Procedures.

8.2.3 *Specimen Preparation, Handling, and Storage*

Blood samples will be collected according to the schedule in Section 7, and will be prepared, handled and stored for future studies following protocols set forth in the study Manual of Procedures.

8.2.4 *Specimen Shipment*

No shipping of specimens is planned for this protocol.

